#### **4.3. Protocol Deviations**

Subjects who did not meet the eligibility criteria for study entry but enrolled in the study will be summarized regardless of whether they were exempted by the sponsor or not. The summary will present the number and percentage of subjects who did not meet at least 1 eligibility criterion and the number of subjects who did not meet specific criteria by treatment group based on the ITT Analysis Set. A by-subject listing will be provided for those subjects who did not meet at least 1 eligibility (inclusion or exclusion) criterion. The listing will present the eligibility criterion (or criteria if more than 1 deviation) that subjects did not meet and related comments, if collected.

Protocol deviations occurring after subjects entered the study are documented during routine monitoring. The number and percentage of subjects with important protocol deviations by deviation reason (eg, non-adherence to andecaliximab/placebo, violation of select inclusion/exclusion criteria) will be summarized by treatment group for the ITT Analysis Set. A by-subject listing will be provided for those subjects with any protocol deviation.

## **5. BASELINE DATA**

### **5.1. Demographics**

Subject demographic variables (ie, age, sex, race, and ethnicity) will be summarized by treatment group and overall using descriptive statistics for age, and using number and percentage of subjects for sex, race, and ethnicity. Age at baseline is calculated in years at the date of randomization. The summary of demographic data will be provided for the ITT analysis set.

In addition, similar summaries by stratum of the stratified randomization will be provided.

A by-subject demographic listing, including the informed consent date, will be provided by subject ID number in ascending order.

### **5.2. Other Baseline Characteristics**

Other baseline characteristics include body weight (in kg), height (in cm), and body mass index (BMI; in kg/m^2). These baseline characteristics will be summarized by treatment group and overall using descriptive statistics for continuous variables and using number and percentage of subjects for categorical variables. For baseline body weight, height, and BMI, descriptive statistics will also be presented by sex in the same table. The summary of baseline characteristics will be provided for the ITT analysis set.

A by-subject listing of other baseline characteristics will be provided by subject ID number in ascending order.

### **5.3. Medical History**

General medical history data will be collected at screening and listed only. General medical history data will not be coded.

A by-subject listing of general medical history will be provided by subject ID number in ascending order.

#### **5.3.1. Disease History**

A summary of disease history will be provided by treatment arms for the ITT analysis set. Variables to be summarized include:

- Primary tumor site
- Histology of gastric cancer
- Disease stage at screening
- Differentiation at screening
- Time since diagnosis (weeks)

These variables will be summarized using number and percentages. The denominator for the percentage of histology of gastric cancer is the number of subjects with gastric cancer. The denominators for the percentage of other variables are the numbers of subjects in the ITT analysis set corresponding to that column.

A by-subject listing of disease history will be provided by subject ID number in ascending order.

In deriving the time since diagnosis, all partial dates of diagnosis will be identified, and the partial dates will be imputed as follows:

- If day is missing but the month and year are available, then the imputed day will be the first day of the month;
- If day and month are missing but year is available, then the imputed day and month will be 01Jan;
- Partial date will not be imputed if the year is missing.

#### **5.4. Prior Chemotherapy and Radiotherapy**

Prior (neoadjuvant or adjuvant) chemotherapy and radiotherapy will be summarized using descriptive statistics by treatment arm using ITT analysis set.

A by-subject listing of prior chemotherapy and radiotherapy will be provided by subject ID number in ascending order.

## 6. EFFICACY ANALYSES

Efficacy analysis will be performed based on the ITT Analysis Set. The investigator assessments will be considered as primary for analyses of efficacy endpoints.

### 6.1. Primary Efficacy Endpoint

#### 6.1.1. Definition of the Primary Efficacy Endpoint

The primary efficacy endpoint of this study is OS, defined as the time from the date of randomization to death from any cause. Subjects who do not have an event will be censored at the last time that subject was known to be alive.

Every attempt will be made to ensure that complete death dates are recorded. In those rare instances where complete death dates are not recorded, the following algorithm will be used:

- If day is missing but the month and year are available, then the imputed day will be the midpoint of the month or the last assessment date + 1, whichever is later.
- If day and month are missing but year is available, then the imputed day and month will be 01Jan or the last day of the latest month that the subject was known to be alive if they have the same year, whichever is later.

#### 6.1.2. Statistical Hypothesis for the Primary Efficacy Endpoint

The primary efficacy hypothesis to be tested is that there is no difference between Treatment Group (Group T) and Control Group (Group C) in OS. Using  $S_T(t)$  and  $S_C(t)$  to denote the OS survival distribution functions of Treatment Group (Group T) and Control Group (Group C), respectively, the statistical hypotheses to be tested in this study will be:

$$H_0: S_T(t) = S_C(t)$$

$$H_1: S_T(t) > S_C(t) \text{ (Group T is superior to Group C in terms of OS)}$$

#### 6.1.3. Analysis of the Primary Efficacy Endpoint

OS in months will be calculated by  $(\text{date of event/censoring} - \text{date of randomization} + 1) / 30.4375$ .

The analysis of OS will be performed using the Kaplan-Meier method for the ITT analysis set. The OS distribution of the 2 treatment arm will be compared using the log-rank test, stratified by the stratification factors at randomization. Medians, Q1, Q3, the proportion of subjects who are alive at 6, 12, 18, and 24 months from randomization will be provided along with the corresponding 95% CI. Kaplan-Meier curves will be provided by treatment arm.

In addition, the hazard ratio (HR) between the 2 treatment arms and its 95% CI will be estimated using the Cox proportional hazards regression model, adjusted for the stratification factors at randomization. The analysis strategy for the situation where there is insufficient information in a stratum is detailed in Section 3.3.

Follow-up time for OS will be summarized as a continuous variable with descriptive statistics by treatment arm.

- For subjects who discontinued study due to lost to follow-up or withdraw of consent, duration of OS follow-up = Date of last follow up – randomization date +1
- For the remaining subjects (including those who die), duration of OS follow up = Date of analysis cut-off date – randomization date +1

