## **6.8. Long-Term Follow-up**

Long-term follow-up (LTFU) for overall survival begins after the EOS visit, or the last visit on study if EOS does not occur. Subjects will be contacted via phone call every 3 months for determination of long term survival status and record of any other anti-cancer therapy, cancer related surgery for up to 5 years after the EOS visit.

Subjects who are not deceased by the time Gilead has made the determination the study will be ended will receive a final follow-up phone call to assess survival status and communicate the Sponsor's decision.

The investigator will make every effort to contact the subject or a close relative or caretaker by phone to collect survival information. The investigator should show due diligence by documenting in the source documents steps taken to contact the subject (ie, dates of phone calls, registered letters, etc).

See Section 3.7 for reasons for discontinuing long-term follow-up and study completion.

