### **3. GENERAL CONSIDERATIONS FOR DATA ANALYSIS**

Data will be summarized using descriptive statistics. For categorical variables, the number and percentage of subjects in each category will be presented; for continuous variables, the number of subjects (n), mean, standard deviation (StD) or standard error (SE), median, first quartile (Q1), third quartile (Q3), minimum, and maximum will be presented.

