## 6.2.3. Analysis for the Secondary Efficacy Endpoints

### 6.2.3.1. Progression-free survival

The analysis of PFS will be performed using the Kaplan-Meier method for the ITT analysis set. The PFS distribution of the 2 treatment arms will be compared using the log-rank test, stratified by the stratification factors at randomization. Medians, Q1, Q3 and the proportion of subjects who are free from disease progression and alive at 6, 12, and 18 months from randomization will be provided along with the corresponding 95% CI. Kaplan-Meier curves will be provided by treatment arm.

In addition, the HR between the 2 treatment arms and its 95% CI will be estimated using the Cox proportional hazards regression model, adjusted for the stratification factors at randomization.

Follow-up time for PFS will be summarized as a continuous variable with descriptive statistics by treatment arm.

- For subjects who are censored from PFS and have discontinued from tumor assessment, duration of PFS follow up = Date of Censoring – randomization date +1
- For the remaining subjects (including subjects with progressive disease [PD] based on RECIST 1.1), duration of PFS follow up = Date of analysis cut-off date – randomization date +1

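### The OS follow-up summary in SAP 6.1.3 runs to the data cut-off for everyone not formally lost or withdrawn, so it reads about 1 to 2 months long and misses unrecorded lapses in survival contact

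*SAP*

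**What the plan says.** SAP 6.1.3 states that "Follow-up time for OS will be summarized as a continuous variable with descriptive statistics by treatment arm". SAP Section 3 lists the statistics used for continuous variables: "the number of subjects (n), mean, standard deviation (StD) or standard error (SE), median", followed by quartiles and range.

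Two bullets in SAP 6.1.3 define the duration:

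- "For subjects who discontinued study due to lost to follow-up or withdraw of consent", follow-up runs from randomization to the date of last follow-up.
- "For the remaining subjects (including those who die), duration of OS follow up = Date of analysis cut-off date", less the randomization date, plus one day.

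The OS variable follows a different rule. SAP 6.1.1 says: "Subjects who do not have an event will be censored at the last time that subject was known to be alive".

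Protocol 6.8 sets the contact schedule after the end-of-study visit: "Subjects will be contacted via phone call every 3 months for determination of long term survival status". It also provides a final call, tied to the sponsor's decision to end the study. Neither document describes a survival status check at the analysis cut-off.

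**The concern.** A living subject has two observation times in the same analysis: last known alive for the Kaplan-Meier curve, and the data cut-off for the follow-up summary. Survival calls are three months apart, so the two dates will often differ.

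Counting everyone to the cut-off would be potential follow-up, which describes how mature the data are. Counting everyone to last contact would be actual follow-up, which describes how complete the data are. The SAP uses the first for most subjects and the second for recorded losses, then takes a plain median. The result is neither measure.

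Readers commonly use median follow-up by arm to judge the maturity of the OS data and whether both arms were followed equally well. As defined, the figure is too long. It also gives no signal if survival contact lapses in one arm without anyone being recorded as lost.

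**Working it through.** **Inputs from SAP 1.3:** control median OS 11.5 months, HR 0.70, accrual 18 months, minimum follow-up 18 months, 10% annual dropout, 430 subjects. **Assumptions added here:** uniform accrual, exponential survival and dropout, and the contact lags stated below.

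**1. The plan's own figures.** The documents state no median follow-up, so the model is checked on events. Schoenfeld: 4 × (1.960 + 1.036)² / (ln 0.70)² = 4 × 8.98 / 0.1272 ≈ 283. With the Protocol Table 8-1 boundaries (Z = 2.509 at 191 events, 1.993 at 286), power at HR 0.70 is 85.0%. Expected deaths by month 36 with 430 subjects are 288. The stated 286 events and 430 subjects are reproduced. In the control arm about 73% have died at month 36, 11% are lost and 16% are alive, so about 89% are credited to the cut-off.

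**2. Median under the SAP rule.** Let λ be the death rate and δ the dropout rate: λ = ln 2 / 11.5 = 0.0603 and δ = −ln(0.9) / 12 = 0.00878 per month. If every dropout is recorded, then for t between 18 and 36 months

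P(follow-up > t) = (36 − t)/18 × [1 − δ/(λ+δ) × (1 − e^(−(λ+δ)t))].

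- Control, t = 25.93: 0.559 × [1 − 0.127 × 0.833] = 0.559 × 0.894 = 0.500. The median is 25.9.
- Drug (λ = 0.0422), t = 25.71: 0.572 × [1 − 0.172 × 0.730] = 0.572 × 0.874 = 0.500. The median is 25.7.

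**3. Reverse Kaplan-Meier, survivors current to the cut-off.** The follow-up curve is e^(−δt) × (36 − t)/18 in both arms. At t = 24.81: 0.804 × 0.622 = 0.500. The median is 24.8. The gaps are 25.93 − 24.81 = 1.1 months (control) and 25.71 − 24.81 = 0.9 (drug).

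**4. Reverse Kaplan-Meier with contact lags (simulated, deaths known to the cut-off).**

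| Last contact of survivors | Control: SAP / reverse KM / gap | Drug: SAP / reverse KM / gap |
|---|---|---|
| Current to cut-off | 25.9 / 24.8 / 1.1 | 25.7 / 24.8 / 0.9 |
| 2-weekly visits if progression-free, 3-monthly calls otherwise | 25.9 / 24.4 / 1.5 | 25.7 / 24.4 / 1.3 |
| All 0 to 3 months before cut-off | 25.9 / 24.0 / 2.0 | 25.7 / 23.8 / 1.9 |

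The middle row takes about two thirds of control survivors as progression-free, from the plan's medians of 9 months (PFS) and 11.5 months (OS).

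**5. Sensitivity to dropout (control arm, all recorded).** The ranges run from current contact to the 0 to 3 month lag. The gap is 0.2 to 1.1 months at 2% annual dropout, 1.1 to 2.0 at 10% and 1.7 to 2.6 at 15%. If none of the 10% dropout is recorded, the SAP median is 27.0 and the gap is 2.2 to 3.0 (up to 3.2 in the drug arm). These are expected gaps. In one arm of 215 subjects the 95% range of the difference is about −1.3 to 3.3 months with current contact, and −0.6 to 4.1 with the 0 to 3 month lag.

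**6. Does the figure react to loss?** Recorded loss: yes. At 10%, 20% and 30% annual dropout the formula in step 2 gives control medians of 25.9, 24.7 and 23.3. Unrecorded lapse: no, as these assumed control-arm scenarios show.

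| Scenario | SAP median | Reverse KM |
|---|---|---|
| No lapse | 25.9 | 24.8 |
| 60% of living subjects silent for 6 to 12 months, the rest 0 to 3 | 25.9 | 22.2 |
| All contact stops 6 months before cut-off | 26.0 | 19.3 |
| All contact stops 12 months before cut-off | 26.1 | 13.8 |

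The SAP median does not fall as contact lapses. In the last two rows it rises slightly, because fewer losses are recorded.

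**The case against.** Crediting deaths to the cut-off is not a mistake in itself. It is a potential-follow-up convention, and reverse Kaplan-Meier also declines to treat a subject who died at 2 months as followed for only 2 months. That stands. The fault lies in combining the convention with actual follow-up for recorded losses, and in crediting living subjects beyond their last contact.

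The lapse scenarios are constructed. Protocol 6.8 requires calls every 3 months with documented effort to reach the subject, and the trial is double-blind. SAP 4.1 tabulates by arm who did not enter or who discontinued long-term OS follow-up, with reasons. Recorded loss also shortens the SAP median itself, as step 6 shows. A reader might infer that the arms will look equally followed whatever happens. The documents do not support that: only a lapse with no loss or withdrawal record is hidden. In the disposition table such a subject would still count as ongoing.

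A reader might also infer from "For the remaining subjects (including subjects with progressive disease [PD] based on RECIST 1.1), duration of PFS follow up = Date of analysis cut-off date" that the PFS summary has the same defect. It does not. The other bullet in SAP 6.2.3.1 uses the actual censoring date for any censored subject who has discontinued tumor assessment, whatever the reason. For a subject with progression, the PFS event has already been observed.

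Finally, no decision in the plan depends on median follow-up. The efficacy analyses are timed by 191 and 286 OS events. That stands, and it limits the point to reporting.

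**Conclusion.** The point holds as a minor defect in a descriptive figure. Under the design assumptions and 10% annual dropout, the SAP median exceeds the reverse Kaplan-Meier median by about 1 month if survivors are current to the cut-off, and by about 2 months if all were last contacted 0 to 3 months earlier. The upper value should not be read as the plan's own figure. No document states that contact lag, and subjects still on treatment are seen every 2 weeks. Across the dropout and recording assumptions tried, the expected gap runs from 0.2 to 3.2 months.

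The summary cannot show a lapse in survival contact that carries no loss or withdrawal record. It would also be wrong to infer that the OS result is biased by this rule. The log-rank test, hazard ratio and curves use last-known-alive censoring and do not change.

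**What to change.** Replace the two OS bullets in SAP 6.1.3, and the sentence introducing them, with a reverse Kaplan-Meier estimate. Use the existing OS time (randomization to death or last known alive), treat death as censored and last known alive as the event, and report the median and 95% CI by arm. As an optional addition, report by arm the time from last known alive to the cut-off among subjects not known to have died, which would show lapses directly. The PFS bullets in SAP 6.2.3.1 need no change for this reason.

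The cost is a short change to the SAP text and one more procedure call on variables already derived. The reported median follow-up will be slightly shorter.

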#### **6.1.4. Sensitivity Analysis of the Primary Efficacy Endpoint**

To assess the robustness of the primary OS results, the following exploratory sensitivity analyses will be performed:

## **6.2. Secondary Efficacy Endpoint**

### **6.2.1. Definition of the Secondary Efficacy Endpoints**

#### **6.2.1.1. Progression-Free Survival**

Progression-free survival is defined as the time interval from the date of randomization to the earlier of the first documentation of definitive disease progression or death from any cause. All scans, whether scheduled or unscheduled, will be considered.

The date of definitive progression will be the time point at which progression is first identified by relevant radiographic imaging data. Data will be censored on the date of last adequate tumor assessment for subjects (including assessments with a not evaluable [NE] outcome):

- who do not have disease progression or die before study discontinuation, or
- who start new anticancer therapy prior to documented disease progression or death, or
- who have  $\geq 2$  consecutive missing tumor assessments before disease progression or death

If a subject does not have a baseline tumor assessment, then PFS will be censored at Study Day 1, regardless of whether or not definitive progression or death has been observed.

PFS in months will be calculated by  $(\text{date of event/censoring} - \text{date of randomization} + 1) / 30.4375$ .

When imaging examinations for one visit are conducted on various dates, the following rules apply for the calculation of the assessment date:

- The response date will be the last date associated with that particular imaging time point.
- The progression date will be the first date associated with that particular imaging time point.

When the date of initiation of anticancer therapy other than the study treatment is incomplete or missing, the following algorithm will be followed:

- If the day is missing but the month and year are available, then the imputed day will be the last day of the month.
- If day and month are missing but year is available, then the imputed day and month will be 01Jan or the last day of the month for the last adequate disease assessment if they have the same year, whichever is later.

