Progression-free survival (PFS) is measured as the interval of time from randomization to the earlier of first documentation of definitive disease progression or death from any cause. Subjects who discontinue the study drug before disease progression will continue to be followed-up until they have documented disease progression.

Objective response is assessed by the RECIST v1.1 as Complete Response (CR), Partial Response (PR), Stable Disease (SD) Non-CR/Non-PD (NN) or Progressive Disease (PD). The response of Not Evaluable (NE) will be recorded for subjects who drop out early before the scheduled imaging is performed, or for images with poor quality. Objective response rate (ORR) is the proportion of subjects who achieve a CR or PR.

Safety

The safety evaluation will be based on incidence of adverse events, clinically relevant changes in laboratory values and vital signs.

Pharmacokinetics

Blood samples to measure GS-5745 and oxaliplatin/5-FU concentrations will be collected at the timepoints specified in the protocol.

Blood samples to measure anti-GS-5745 antibodies will also be collected at the time points specified in the protocol.

Pharmacodynamic and Exploratory Biomarkers

CCI [REDACTED]

---

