- PFS: Data from surviving, non-progressing subjects will be censored at the earliest of the time of initiation of antitumor treatment other than the study treatment or the last time that lack of definitive progression was objectively documented. Data from subjects who have disease progression or die after  $\geq 2$  consecutive missing tumor assessments will be censored at the last time prior to the missing assessments that lack of definitive disease progression was objectively documented.
- DOR: Data from surviving, non-progressing subjects will be censored at the earliest of the time of initiation of antitumor treatment other than the study treatment or the last time that lack of definitive disease progression was objectively documented. Data from subjects who have disease progression or die after  $\geq 2$  consecutive missing tumor assessments will be censored at the last time prior to the missing assessments that lack of definitive disease progression was objectively documented.

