##### 4.4.2. Missing assessments and inevaluable designation

When no imaging/measurement is done at all at a particular time point, the patient is not evaluable (NE) at that time point. If only a subset of lesion measurements are made at an assessment, usually the case is also considered NE at that time point, unless a convincing argument can be made that the contribution of the individual missing lesion(s) would not change the assigned time point response. This would be most likely to happen in the case of PD. For example, if a patient had a baseline sum of 50 mm with three measured lesions and at follow up only two lesions were assessed, but those gave a sum of 80 mm, the patient will have achieved PD status, regardless of the contribution of the missing lesion.

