#### 6.2.1.2. Objective Response Rate

Objective response rate is defined as the proportion of subjects with best overall response during andecaliximab therapy of complete response (CR) or partial response (PR) based on RECIST 1.1. Subjects, who do not have sufficient baseline or on-study tumor status information to be adequately assessed for response status (ie, those with best overall response of NE or no disease [ND]) or received anticancer therapy other than the study treatment prior to achieving CR or PR, will be considered as non-responders and will be included in the denominators in calculations of response rates.

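### SAP 6.2.1.1 lets a not-evaluable scan set the PFS censoring date, which contradicts Protocol 8.4.1 and is not declared in SAP 2.4

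*SAP*

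**What the plan says.** SAP 6.2.1.1 fixes the PFS censoring date for three groups: subjects with no event, subjects who start new anticancer therapy before an event, and subjects with two or more "consecutive missing tumor assessments before disease progression or death". For all three the rule is: "Data will be censored on the date of last adequate tumor assessment for subjects (including assessments with a not evaluable [NE] outcome". The SAP defines neither an adequate nor a missing assessment.

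Protocol 8.4.1 censors subjects who are alive without progression at the earlier of new antitumor treatment and "the last time that lack of definitive progression was objectively documented". A subject who progresses or dies after two or more missing assessments is "censored at the last time prior to the missing assessments that lack of definitive disease progression was objectively documented".

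On the meaning of NE, the efficacy criteria in the Protocol Synopsis say that it "will be recorded for subjects who drop out early before the scheduled imaging is performed, or for images with poor quality". The RECIST text in Protocol Appendix 7 (section 4.4.2) says: "When no imaging/measurement is done at all at a particular time point, the patient is not evaluable (NE) at that time point". It adds that a time point with only some lesions measured is usually NE as well.

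SAP 2.4 (changes from the protocol) and the revision table in SAP 13 mention only the PD-L1 subgroup.

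**The concern.** The protocol asks for evidence that the disease had not progressed. The SAP accepts a time point whose recorded outcome says that this could not be determined. The two documents therefore give different censoring dates for the same subject, and the SAP does not present the difference as a change. PFS is the first secondary endpoint in the testing sequence, at one-sided 0.016, so its derivation should not depend on which document the programmer follows. If scans become unreadable more often in one arm, the choice can move the estimated hazard ratio.

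**Working it through.** **1. The two rules side by side.** An NE scan is incomplete, of poor quality or not done. None of these objectively documents absence of progression, so under Protocol 8.4.1 an NE scan cannot set the censoring date. Under SAP 6.2.1.1 it can. The conflict is explicit and needs no inference.

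**2. The plan's own PFS figure.** Inputs from SAP 1.3: 322 events, HR 0.70, one-sided alpha 0.016, control median 9 months, 430 subjects, 18 months accrual plus 18 months follow-up, 10% annual dropout.
- Power = Φ(½·√322·|ln 0.70| − z₀.₀₁₆) = Φ(3.200 − 2.144) = Φ(1.056) = 85.4%, against 85% stated.
- Expected events with exponential times: 321.0 with dropout hazard −ln(0.9)/12 per month, or 322.4 with 0.1/12, against 322 stated.

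The design figures reproduce and are not in dispute.

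**3. Size for one subject.** Take the nominal days in SAP Table 3-3 and the SAP conversion of 30.4375 days per month. The subject has an evaluable non-progression scan on day 57, NE on days 113 and 169, and no further data.
- SAP date: 169/30.4375 = 5.55 months.
- Protocol date: 57/30.4375 = 1.87 months.
- Difference: 112/30.4375 = 3.68 months. With one trailing NE it is 56/30.4375 = 1.84 months.

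Only trailing NEs matter. An NE followed by an evaluable non-progression scan changes nothing under either rule.

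**4. Size for the trial.** The documents give no NE rate, so rates of 0% to 20% per time point were assumed. The simulation uses the SAP 1.3 inputs, scans every 8 weeks, progression dated at the first evaluable scan, 20% of events assumed to be deaths, and NE independent of disease state.

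Hazard ratio with unequal NE rates (0.711 with no NE; progression is seen only on an 8-week grid, so this is not exactly 0.70):

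| NE rate, control / treatment | SAP rule | Parenthetical deleted | Deleted, and NE also counted as missing |
|---|---|---|---|
| 5% / 20% | 0.696 | 0.702 | 0.669 |
| 20% / 5% | 0.732 | 0.726 | 0.759 |

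Deleting the parenthetical moves the HR by 0.006 towards the no-NE value in both rows and loses no events. Also counting NE as missing moves it further away in both rows.

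With equal NE rates (a separate run, 100,000 per arm), the SAP rule was compared with NE counted as missing:

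| NE rate, both arms | HR: SAP rule | HR: NE as missing | Events per 430: SAP rule | Events per 430: NE as missing |
|---|---|---|---|---|
| 5% | 0.713 | 0.713 | 315.3 | 313.7 |
| 10% | 0.710 | 0.709 | 314.6 | 308.4 |
| 20% | 0.712 | 0.708 | 313.3 | 290.5 |

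At 20% NE, counting NE as missing discards 313.3 − 290.5 = 22.8, or about 23, observed events. Differences of a few thousandths between rows are within simulation error. Comparisons within a row use the same simulated subjects.

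**The case against.** The best defence is that an NE scan is not empty. RECIST Table 1 in Appendix 7 assigns NE when target lesions are not all evaluated even though non-target disease has not progressed and there is no new lesion. Section 4.4.2 allows progression to be called on incomplete measurements. That stands, but progression in the unmeasured target lesions is not excluded, so the protocol's standard is still not met. SAP 6.2.1.2 also treats NE as insufficient information, but there NE is a best overall response for the whole subject. It does not contradict a rule about single time points, and this point does not rest on it. The list of PFS sensitivity analyses in SAP 6.2.4 is not visible in the public copy, so one may already address NE.

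Three stronger readings are tempting, and the documents do not support them.

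- *A reader might infer that missed scans coded NE count as adequate and so escape the missed-scan rule.* The Synopsis and RECIST do code an undone scan as NE. But the SAP names NE and missing separately, derives assessment dates from imaging dates, and would have a missed-scan rule that never applied if every missed scan were adequate. This is one reading of an undefined term. Nor does Protocol 8.4.1 say that a performed NE scan is missing. The ambiguity is real, since SAP 3.6.1 lists unusable data among reasons for a missing data point, and one sentence would settle it.
- *A reader might infer that every dropout carries an NE date.* Under the plan's assumptions about 9.1% of control and 11.3% of treated subjects drop out before a PFS event: 215 × (0.091 + 0.113) = about 44 of 430. That counts dropouts, not dated NE scans. A scan never done has no imaging date.
- *A reader might infer that the rule lengthens median PFS by 20% (1.84/9) or favours the experimental arm.* The 20% compares one censored subject's shift with the median and is not a shift of the median. In simulation the HR moved in either direction, depending on which arm had more NE.

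**Conclusion.** The contradiction between SAP 6.2.1.1 and Protocol 8.4.1 is established from the text, and SAP 2.4 does not declare it. For an individual censored subject it is worth nominally up to 1.84 months for one trailing NE and 3.68 months for two. For the trial the effect is small: about 0.006 on the HR when NE rates are 5% and 20% in opposite arms. That figure rests on assumed NE rates, an assumed 20% share of deaths, and NE unrelated to disease state. If scans become unreadable because patients are worsening, the simulation does not describe it. No direction of bias is shown. The primary OS analysis is unaffected, and PFS is tested formally only if OS succeeds. How performed NE scans should count in the two-consecutive-missing rule is a separate choice with a real trade-off, and the protocol does not settle it.

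**What to change.** In SAP 6.2.1.1:

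1. Delete the parenthetical that includes NE outcomes.
2. Define an adequate assessment, for the censoring date, as one with an overall time-point response of CR, PR, SD or Non-CR/Non-PD. This matches Protocol 8.4.1.
3. State that a scan not performed counts as missing for the two-consecutive-missing rule, however its response is coded.
4. Do not count performed NE scans as missing in the main analysis. Run that convention as a sensitivity analysis, because it discards observed progressions and deaths.

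If the sponsor prefers to keep the present rule, it should declare and justify it in SAP 2.4 and report the protocol rule alongside.

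The cost is a few lines of SAP text and one derivation flag. Some censoring dates move earlier. Deleting the parenthetical removes no events, and no new data are needed.
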